2.4 Study Products

The treatment regimen is:

- i. Optive® Fusion a CE marked eyedrop, manufactured by Allergan Pharmaceuticals Ireland, containing 0.1% sodium hyaluronate, 0.5% carmellose sodium and 0.9% glycerol for daytime use. The eyedrop will be used as needed up to four times a day but at least twice a day;
- ii. Optive® Gel Drop a CE marked gel manufactured by Allergan Pharmaceuticals Ireland, containing 0.5% carboxymethylcellulose sodium and 0.9% glycerol for night time use. The eyedrop will be used once in the evening; the gel drop being instilled any time during the last hour prior to sleep.

The treatment regimen is to be used for one month (30 ± 3 days).

2.5 Study Design

The study is conducted as an open label, bilateral, prospective, interventional single arm clinical study, however, the investigator carrying out the tear film kinetics and tissue staining analyses post-hoc are masked for these activities.

The participants attend a total of three scheduled visits over a five-week period.

- i. Enrolment visit;
- ii. Baseline / Dispensing visit (7 ± 1 days from enrolment);
- ii. One-month follow-up visit (30 ± 3 days from dispensing).

3 Analysis

3.1 Database

The final analysis for the CSR concerns the closed-out database when all participants have been exited from the study.

3.2 Data Sets

Three data sets will be produced as defined below:

- i. Safety Analysis Data Set
Safety analyses will be conducted using this data set. The Safety Analysis Data Set will include all the participants enrolled into the study.
- ii. Full Analysis Data Set

The Full Analysis Data Set will include of all participants who have been exposed to any product evaluated in this study.

iii. Per protocol Data Set

The Per Protocol Data Set will include all the participants who have completed the study as per the protocol, this set will include only participants who have completed the study without any major deviation judged to affect the validity of the data.

Listings and descriptive statistics will be produced for the latter two data sets and comparative statistics will only be produced for the Per Protocol Data Set.

3.3 *Normality Testing*

All primary and secondary endpoints, being continuous endpoints, will be checked for normality graphically and by statistical tests prior to the comparative statistics being carried out. The Q-Q Probability plot will be used to examine the values against a normality distributed data. Statistical (Normality) testing will be carried out by Kolmogorov Smirnov, and Shapiro Wilk tests. The derived histograms and the values of kurtosis and skewness will be taken into consideration when verifying normality and deciding upon the statistical model to use

If the normality assumption does not hold, the data will be transformed; the transformation method chosen will depend upon the skewness and the kurtosis values. The following transformations are the key transformation methods that will be considered for the recorded variables the transformations will be carried in the following order until normality or near normality is achieved: square root, logarithm and inverse. If the data after applying transformations differs statistically from normal, then a non-parametric model will be used.

3.4 *Descriptive Statistics*

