3.4.1 General

For all the key parameters recorded, summary tables including descriptive and/or distribution statistics will be given for both the per protocol analysis and the full analysis data sets.

All enrol participants, defined as subjects who signed the consent form will constitute the safety data set. All subjects who meet the eligibility criteria, adhere to the protocol, and successfully complete the full study assessment will be available for the per-protocol analysis. Participants with missing data will be included in the analysis unless there is some non-response-related reason to exclude them, such as a protocol violation/invalid data.

For continuous variables, the following descriptive statistics will be reported: mean, median, standard deviation, minimum, maximum and sample size. For ordinal variables, the following statistics will be reported: median, mode, minimum, maximum, quartiles, sample size and distribution tables will be produced.

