3.4.2 Output

The descriptive statistics will be reported both for the full analysis population and the per protocol population.

3.5 *Comparative Statistics*

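### All tests and confidence intervals are confined to the Per Protocol set, so no inferential estimate of the treatment effect includes participants excluded for deviations

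*SAP*

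**What the plan says.** SAP 3.2 defines three data sets and closes by stating that "comparative statistics will only be produced for the Per Protocol Data Set". All comparisons for the two primary endpoints and the secondary endpoint are set out in SAP 3.5, and nothing there names another set.

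Membership of the Per Protocol set is described in two places:

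- SAP 3.2 first says "The Per Protocol Data Set will include all the participants who have completed the study as per the protocol", then narrows the ground for exclusion: "this set will include only participants who have completed the study without any major deviation judged to affect the validity of the data".
- SAP 3.4.1 says that eligible subjects who "adhere to the protocol, and successfully complete the full study assessment will be available for the per-protocol analysis". It adds: "Participants with missing data will be included in the analysis unless there is some non-response-related reason to exclude them", and gives a protocol violation or invalid data as such a reason. Protocol 7.1 (Statistical Analysis Plan) has the same two sentences in almost the same words.

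The Full Analysis set covers all "participants who have been exposed to any product evaluated in this study". Its role is descriptive: "The descriptive statistics will be reported both for the full analysis population and the per protocol population". For continuous variables SAP 3.4.1 lists the mean, median, SD, minimum, maximum and sample size. It lists no change score, interval or test.

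On timing, SAP 3.1 says only: "The final analysis for the CSR concerns the closed-out database when all participants have been exited from the study".

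**The concern.** Whether a participant enters the Per Protocol set is settled after baseline, by completing the study and by a judgement about deviations. Protocol 5.4 includes adverse events among the grounds for withdrawal, so leaving the set can be related to treatment. SAP 3.5.1 confirms that efficacy is the change from the dispensing visit to the 30-day visit with no control group. There is no second arm in which similar exclusions might offset the effect.

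The judgement that removes a participant is not dated in the text available. Protocol 12.4 has compliance reviewed throughout and non-compliance recorded, and Protocol 13.2 gives examples of major and minor deviations. Neither places the final validity decision before outcomes are seen. The staining images are read masked to participant and visit (Protocol 6.3.2), but OSDI and the waking VAS are open-label self-reports.

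The first primary objective (Protocol 2.2) is to quantify an effect. If those excluded responded differently, the reported size and its interval describe a selected group, with no modelled counterpart on the wider group to compare.

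**Working it through.** **The plan's own figure.** Protocol 7.1 (Determination of Sample Size) gives n = 27, one-sided alpha 0.05, margin 7.5, true OSDI difference 10.0 and SD 5.0, for 81% power. A one-sided paired t-test has noncentrality (10.0 − 7.5)/5.0 × √27 = 2.598 on 26 df, which gives 81.2%. The figure reproduces, so the sample-size inputs are usable below.

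**Inputs.**
- 35 participants enter the investigational phase and 30 complete per protocol (Protocol 5.2). The gap of 5 (14.3%) is a planning allowance, not a count of deviators.
- Mean OSDI improvement in the 30 is taken as 10, the planning value.
- Assumption: k of the 5 are deviators with both visits and mean improvement x. The others have no follow-up.

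**Shift from leaving the deviators out.** The mean of all with both visits is (30 × 10 + k·x)/(30 + k). The Per Protocol mean exceeds it by k(10 − x)/(30 + k).

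| k | x = 5 | x = 0 | x = −5 |
|---|---|---|---|
| 1 | 0.16 | 0.32 | 0.48 |
| 2 | 0.31 | 0.63 | 0.94 |
| 3 | 0.45 | 0.91 | 1.36 |
| 5 (upper bound) | 0.71 | 1.43 | 2.14 |

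The shift is zero if k = 0 or x = 10. It reverses if deviators do better: k = 2 and x = 15 gives −0.31. A dropout with only a baseline value adds about nothing that a different analysis set could recover.

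**Scale.** The 95% CI half-width at n = 30 is 2.045 × SD/√30.
- If 5.0 is the SD of the change: 1.87 points.
- If 5.0 is the SD of a single measurement, with independent visits, the SD of the change is 5√2 = 7.07: 2.64 points.
- k = 2, x = 0: 0.625/1.867 = 33%, or 0.625/2.640 = 24%.
- k = 5, x = 0: 1.429/1.867 = 77%, or 1.429/2.640 = 54%.

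**Significance against zero.** With f = k/(30 + k), the SD in the wider group is √(SD² + f(1 − f)(10 − x)²). The worst case is k = 5, x = −5, SD 7.07: √(50 + (5/35)(30/35) × 225) = 8.81, so t = 7.857/(8.81/√35) = 5.28. Significance survives in every case in the table.

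**Against the 7.5-point planning margin.** With SD 5, the two-sided 95% lower bound in the 30 is 10 − 1.87 = 8.1. Adding two deviators with x = 0 gives mean 9.375, SD √(25 + (2/32)(30/32) × 100) = 5.56 and lower bound 9.375 − 2.040 × 5.56/√32 = 7.4. With SD 7.07 the bound in the 30 is already 10 − 2.64 = 7.4. The SAP does not test this margin, so this bears on how the estimate reads, not on a planned decision.

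**Do the two Per Protocol descriptions agree?** Not fully. A completer with minor non-adherence stays in under the major-deviation wording of SAP 3.2, but could be left out under the adherence wording of SAP 3.4.1. A completer who only missed a non-critical measurement is kept by the missing-data sentence. That sentence itself sits uneasily beside a set restricted to completers.

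**The case against.** The strongest reply is that the choice is open and consistent. The protocol names only a per-protocol analysis and recruits to obtain 30 completers. There is no randomisation for a full-set analysis to protect, and a completer analysis is one reading of the effect of a month's treatment. Only major deviations judged to affect validity lead to exclusion, deviations are documented as they arise, and the staining reading is masked. Full Analysis descriptives by visit would let a reader subtract means. The sizes above are hypothetical, cover only OSDI and leave significance intact.

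Much of this stands as a limit on magnitude. The documents support no figure for k or x, nothing can be quantified for staining or VAS, and some SAP pages were not available, so the timing point rests on the text that was.

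It does not remove the concern. Declaring the set in advance does not undo post-baseline selection; it makes the selected estimate the only inferential one. Subtracting visit means can compare different people at each visit and yields no interval for the change. The missing-data sentence does not bring deviators back, because it exempts protocol violations.

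A fair point about the remedy is that a full-set analysis can admit participants enrolled outside the entry criteria. The retained Per Protocol analysis shows the effect of leaving them out.

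**Conclusion.** The concern holds. Every planned test, model difference and confidence interval rests on a set chosen partly by post-baseline events, and no inferential estimate on a wider set is planned.

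The likely effect is on the size of the estimate. With one to three deviators who have both visits and improve by 5 points, do not change or worsen by 5, the Per Protocol OSDI mean would be 0.2 to 1.4 points too high. The upper bound, with all five of the planning allowance, is 2.1. The bias could be zero or run the other way. These are raw OSDI points, whereas SAP 3.5.2 reports model differences in percentage. They assume a mean improvement of 10 in the 30 retained participants. The conclusion against zero change is not at risk under any of these assumptions.

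This should be changed, because the correction is cheap and bears on the quantity the study sets out to report. The restriction itself is certain; its numerical effect is not.

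**What to change.** 1. In SAP 3.2, define the Full Analysis set as participants dispensed test product at Visit 2 who have a baseline value. The present wording can be read to admit people who used only the run-in product.
2. Make that set the main one for comparative statistics: the planned mixed models on all available data, and the paired t-test or Wilcoxon test on all participants with both visits, whatever their deviations.
3. Keep Per Protocol as a supporting analysis with a single definition that replaces those in SAP 3.2 and 3.4.1 and says how missing data are handled within it. Align the matching sentences in Protocol 7.1 (Statistical Analysis Plan).
4. State that the Per Protocol exclusion list, with reasons, is fixed and documented before outcomes are reviewed.

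The cost is SAP wording, a small protocol consistency edit and one extra run of analyses already planned, with no new data collection. The main estimate may be slightly less favourable. The change restores deviators who have follow-up data; it does not recover dropouts without it.

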5.4 Premature Withdrawal

A participant will be withdrawn from the investigation before completion if:

- i. The participant withdraws his/her consent to be included in the trial;
- ii. An adverse event takes place that is considered by the participant or the investigator to warrant withdrawal;

- iii. Any event that leads the investigator to believe that it is not in the best interest for the participant to continue in the study;
- iv. The study is prematurely terminated by the Principal Investigator, local research ethics committee or the Sponsor;
- v. The participant is lost to follow-up;
- vi. The participant no longer meets the eligibility criteria;
- vii. The participant dies.

5.5 *Informed Consent*

Each participant must give written consent according to local requirements after the nature of the study has been fully explained. The consent form must be signed before performance of any study-related activity. The consent form that is used must be approved by both the Sponsor and by the reviewing IEC. The informed consent must be in accordance with principles that originated in the Declaration of Helsinki, current ICH and GCP guidelines, applicable regulatory requirements, and sponsor policy.

Before entry into the study, the Investigator or an authorized delegated member of the investigational staff must explain to potential participants the aims, methods, reasonably anticipated benefits, and potential hazards of the study, and any discomfort it may entail. Participants will be informed that their participation is voluntary and that they may withdraw consent to participate at any time. They will be informed that choosing not to participate will not affect the care the participants will receive. Finally, they will be told that if needed their records may be accessed by health authorities and authorized sponsor staff without violating the confidentiality of the participant, to the extent permitted by the applicable law(s) or regulations.

The participants will be given sufficient time to read the informed consent form and the opportunity to ask questions. After this explanation and before entry into the study, consent must be appropriately recorded by means of the participant's dated signature. After having obtained the consent, a copy of the informed consent form must be given to the participants.

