In the event that additional investigators / sites are added to the protocol, the informed consent will be modified to include the Investigator's name, address, phone number and 24-hour emergency number.

6 Study Design & Procedures

6.1 *General Description*

The study will be conducted as an open label, bilateral, prospective, interventional single arm clinical study, however, the investigator carrying out the tear film kinetics and tissue staining analyses post-hoc will be masked for these activities.

6.2 *Experimental Routine*

The participants will attend a total of three scheduled visits over a five-week period.

- i. Enrolment visit;
- ii. Baseline / Dispensing visit (7 ± 1 days from enrolment);
- ii. One month follow-up visit (30 ± 3 days from dispensing).

The participants will attend an initial Enrolment visit to obtain their informed consent, evaluate their suitability to take part in the investigation and collect their baseline information. The participants who fulfil the investigation inclusion and exclusion criteria will be dispensed with the run-in eyedrops to be used for one

week. Subjects who wear contact lenses will be required to cease wear during this run-in period (and continue to do so for the duration of the study). At the completion of the one-week run-in period the participants will attend the clinic for baseline measurements and dispensing of the study products. The participants will use the study products as per the study protocol for the remainder of the study. The Baseline and One-month visits will be scheduled in the morning. The participants will not take part in any concomitant investigation of any type or take concomitant medications not allowed by the exclusion criteria.

The participants will complete weekly time stamped questionnaires sent in electronic format using [REDACTED] secure electronic survey software using either a personal computer, Apple Mac, tablet or smart phone to characterise the time scale of the improvement that may be achieved.

Two visual analogue scale questionnaires will be sent on each occasion: one overnight to capture symptomatology upon waking and one late afternoon to be completed prior to sleep to capture daytime and evening symptomatology. In addition, the participants will complete the OSDI questionnaire one and four weeks after test product dispensing.

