7.1 Determination of Sample Size

A sample size of 27 achieves 81% power to detect superiority using a one-sided t-test when the OSDI margin of equivalence is 7.5 and the true difference between the baseline and the follow-up value is 10.0, the data being drawn from a single population with a within participant standard deviation of 5.0 and with the significance level (alpha) of the test being set at 0.050. Based upon the intended cohort sample it is proposed to screen 40 participants to have 35 participants enrolled into the investigational phase at the end of Visit 2 to achieve a cohort of 30 participants completing the study as per the protocol.

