3.5.1 General

The study design does not include a control group the efficacy of the regimen will be measured by comparing the data recorded at the dispensing visit, prior product dispensing visit (Baseline) to the data recorded at the 30-Day follow-up visit (Response).

In this study two sets of analyses will be carried out for each primary and secondary variables. The first set will follow a linear model approach to account for all the data characteristics (e. g. multiple data for the same response variable for a given timepoint). The second set will be based on simplistic testing such as the t-test or if not applicable an equivalent non-parametric test.

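### SAP 3.2 leaves completers with a validity-affecting major deviation out of every planned comparison; a supportive Full Analysis comparison should be added

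*SAP*

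**What the plan says.** SAP 3.2 defines three data sets. The safety set holds everyone enrolled. For the second, "The Full Analysis Data Set will include of all participants who have been exposed to any product evaluated in this study". The Per Protocol set holds participants who completed as planned and had no major deviation thought to undermine the validity of their data. The last two sets get listings and descriptive statistics, but "comparative statistics will only be produced for the Per Protocol Data Set".

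SAP 3.4.1 restates the Per Protocol requirement as eligibility, adherence and completion of the full assessment. It then adds: "Participants with missing data will be included in the analysis unless there is some non-response-related reason to exclude them". It names no method.

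SAP 3.5.1 says "The study design does not include a control group", so efficacy is the baseline to 30-day change. SAP 3.5.2 models OSDI total score and lissamine green staining with a mixed model that has two time levels, baseline and one month. Protocol 2.2 words the first primary objective as quantifying the effect on symptoms.

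**The concern.** With no comparator, the efficacy result is the mean change itself, so the choice of who enters that mean matters directly. A completer with a validity-affecting major deviation has a baseline value and a one-month value, yet contributes to no estimate of change and no confidence interval.

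The exclusion depends on a judgement, and the readable SAP does not say who makes it or when. Treatment is open label (Protocol 6.1). Masked image reading (Protocol 6.3.2) protects the staining measurement, but it does not govern who is placed in the analysis set. If the excluded completers improved less than the rest, the reported improvement would be too large, and no planned estimate would show by how much. If they improved more, it would be too small.

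The size of the effect is at stake, not whether a change is detected.

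**Working it through.** **1. The plan's own figure.** Inputs from Protocol 7.1: n = 27, one-sided alpha 0.05, SD 5.0, and power calculated "when the OSDI margin of equivalence is 7.5 and the true difference between the baseline and the follow-up value is 10.0".

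- Standardised effect = (10.0 − 7.5)/5.0 = 0.5.
- Noncentrality = 0.5 × √27 = 2.60, with 26 degrees of freedom and critical t = 1.706.
- Power = 0.812, which matches the stated 81%. So 5.0 acts as the SD of the within-participant change.

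**2. Is significance at risk?** SAP 2.2 compares the two visit means with no margin, so the reference is zero change. With the target of 30 Per Protocol participants:

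- Standard error = 5.0/√30 = 0.91.
- t = 10.0/0.91 = 10.95.
- 95% half-width = 2.045 × 0.91 = 1.87 points.

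A few excluded participants cannot overturn this.

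**3. Who is in which analysis?**

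| Participant | One-month value | Full Analysis descriptives | Planned comparison |
|---|---|---|---|
| Completer, no validity-affecting major deviation | yes | yes | yes |
| Completer with such a deviation | yes | yes | no |
| Withdrawn after dispensing, before one month | none stated in readable text | baseline only | no |
| Left after run-in drops only | no | possibly, by the wording of SAP 3.2 | no |

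The missing-data sentence in SAP 3.4.1 does not change the last column. It follows a sentence that limits the Per Protocol analysis to people who completed the full assessment, and Per Protocol is the only set compared.

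**4. Size for the second row.** Let j be the number of such completers, and g the amount by which their mean improvement falls short of the Per Protocol mean. With 30 in the Per Protocol set:

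overstatement = j × g / (30 + j)

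The documents give neither j nor g. For scale only, assume j = 1 or 2 and g = 5, 10 or 15 points (one, two or three planning SDs):

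- j = 1: 5/31 = 0.16, 10/31 = 0.32, 15/31 = 0.48.
- j = 2: 10/32 = 0.31, 20/32 = 0.63, 30/32 = 0.94.

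These values show how the formula behaves. They are not estimates, and a negative g reverses the sign. No figure in mm² is possible for staining, because the documents give no expected change or SD.

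**5. What the mixed model can recover for the third row.** With two time points and k of 35 participants having only a baseline, the estimated change is approximately

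completers' change + (b − 1) × (k/35) × (baseline mean of the k − baseline mean of completers)

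where b is the slope of follow-up on baseline. If the baselines are equal, the second term is zero. As an example, assume a baseline SD of 12 at both visits (not in the documents) and a change SD of 5.0. Then b = 1 − 25/(2 × 144) = 0.913. With k = 2 and a baseline gap of 10 points, the term is −0.087 × 0.057 × 10 = −0.05 points. So baseline-only participants hardly move the estimate, whatever their unobserved outcome.

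**The case against.** **The exclusion is already visible.** Listings and descriptive statistics are planned for the Full Analysis set as well, so a reader can compare visit means between the sets. This stands in part. But the Full Analysis baseline mean includes people with no one-month value, so the difference between its visit means is not a within-participant change. It also has no confidence interval.

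**Per Protocol is a deliberate choice.** Protocol 5.2 and 7.1 set the target as participants completing as planned, which is reasonable for a small post-marketing study. This also stands, and is why the added analysis should be supportive only.

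**The effect is probably small.** A shift of a few tenths of a point lies well inside a half-width of 1.87. This is fair, and it limits the priority of the point.

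**A stronger reading.** A reader might infer that Protocol 5.4 discards the outcomes of participants withdrawn for an adverse event or in their best interest, that this inflates the result by a calculable amount, and that a Full Analysis comparison would correct it. One or two such withdrawals among 35, with assumed changes of +5 to −5 points instead of 10.0, would shift the mean by 1 × 5/35 = 0.14 to 2 × 15/35 = 0.86 points. The documents do not support this reading, for three reasons:

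- The scheduling text after Protocol 6.4.3 is redacted, so an exit assessment cannot be excluded.
- The counts and outcomes are invented.
- By step 5 of the working, the two-time-point model leaves that shift almost unchanged. The questionnaires in Protocol 6.2 ("the participants will complete the OSDI questionnaire one and four weeks after test product dispensing") do not help, because the week-one value is not in the model.

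Recalling withdrawn participants at one month is not recommended either. It would need an ethics-approved amendment. The values would mix time off product, resumed drops and other treatment, which a single-arm study cannot separate.

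**Conclusion.** The point holds as a low-cost improvement to the SAP. Every planned estimate of change excludes completers with a validity-affecting major deviation, although their data exist, and no supportive estimate includes them.

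The bias is favourable only if those participants did worse than the ones analysed. Its size cannot be stated from the documents. Significance against zero is secure if the planning values (change 10.0, SD 5.0, 30 participants) are roughly right.

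The point does not extend to a quantified bias from adverse-event or best-interest withdrawals. The proposed analysis would not remove such a bias if it existed.

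**What to change.** Amend SAP 3.2 before the database is closed:

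- Run the baseline to one-month comparison of both primary endpoints on the Full Analysis Data Set as well. For this purpose, restrict it to participants dispensed test product at Visit 2 who have a baseline value. The restriction is needed because the current definition could admit people exposed only to the run-in drop.
- Use the mixed model in SAP 3.5.2 with all available data, including completers with major deviations. Report the estimate and 95% confidence interval as supportive, beside the Per Protocol result.
- State that participants withdrawn without a one-month value add almost nothing to this estimate, so it does not remove bias from adverse-event or best-interest withdrawals. Report their number and reasons.

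The cost is a few sentences in the SAP and one extra run of an already specified model per endpoint. No visit or procedure changes. The downside is that the supportive estimate includes data from participants with deviations, some of which may be of doubtful validity. The Per Protocol result remains the description of those treated as planned.
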